#### **Procedures for donors with incident infection identified through LAg Avidity assay (serology and NAT concordant positive, with LAg Avidity results)**

LAg avidity testing will be performed in real time along with routine SANBS supplementary testing and the test results will be available at the time of notification of positive test results. All donors with concordant results, both LAg avidity negative and positive, will initially be counseled in accordance with the SANBS standard procedures which includes the performing of an HIV rapid test when the donor returns for counseling.

The donors with an incident HIV infection identified through the LAg Avidity assay will be assessed for suitability to be enrolled on to the study. If the donor satisfies the inclusion criteria for this study, consent will be sought and the donor enrolled. Blood samples will be collected and the ACASI questionnaire completed.

All other HIV positive donors (serology only and/or non-recent concordant infections) will complete the standard SANBS HIV risk inventory survey as part of the standard SANBS operational procedure.

#### **4.2.2. Control Recruitment and Enrollment**

SANBS collection sites are administratively organized into zones, branches, and clinic sites. Clinics can be fixed or mobile collection sites. To meet the study criterion of matching by geographic area, controls will be selected from clinics within the branches from where persons with recently acquired HIV infection have been identified. To minimize selection bias, clinics within each branch will be randomly selected by the study statisticians. On recruitment days at the randomly selected clinics, individuals that are demographically matched potential controls (age within 5 years, and by population group) will be randomly selected using systematic sampling and approached for enrollment into the study as a “potential control”. Our study documents and consents indicate the “potential control” designation, and explain the meaning of this term. Following successful donation the potential controls will be invited to complete the ACASI study questionnaire. After each donation has been tested and if the donor tests negative for all infections, the person will be reclassified in the database as a control.

The characteristics of individuals with recent HIV and HBV infection (per NAT-only over a 5 year period) are substantially similar for the three matching variables for the study cases and controls (see Table 3). As such, we intend to use a subset of the controls matched for the HIV portion of the study to serve as controls for the HBV objective.

Table 3. Demographic characteristics of HIV NAT only and HBV NAT only positive donors at SANBS for the years 2006 – 2010.

Demographic Characteristic		HIV (n=300)		HBV (n=248)	
		Number	Percent	Number	Percent
Gender	Female	174	58.0	108	43.5
	Male	126	42.0	139	56.0
	Missing	0	0.0	1	0.4
Population Group	Asian	6	2.0	12	4.8
	Black	251	83.7	161	64.9
	Coloured	12	4.0	10	4.0
	White	29	9.7	63	25.4
	Missing	2	0.7	0	0.0
Age Group	16-19 years	49	16.3	43	17.3
	20-25	90	30.0	69	27.8
	26-30	59	19.7	43	17.3
	31-40	60	20.0	52	21.0
	41-50	32	10.7	24	9.7
	51-60	10	3.3	10	4.0
	61-70	0	0.0	7	2.8
SANBS Region	Eastern Cape	24	8.0	18	7.3
	Egoli (Johannesburg)	43	14.3	34	13.7
	Free State/Northern Cape	29	9.7	28	11.3
	KwaZulu Natal (Durban)	83	27.7	60	24.2
	Mpumalanga	35	11.7	30	12.1
	Northern (Pretoria)	52	17.3	31	12.5
	Vaal	34	11.3	47	19.0

There are two reasons why we believe that the controls for the HIV cases can serve the dual purpose as the control for the HBV cases. First, we expect the distribution of HBV cases to be similar to the distribution of HIV cases for geography, population group, and age. Second, because there will be more HIV-controls in the database, for each HBV case even if the characteristics of specific HBV and HIV cases do differ, there should still be an adequate number of controls to match on geography, population group, and age for the HBV study within the already selected HIV study matched controls to achieve a similar case control ratio of 1:3 HBV case to controls ratio. The study team will be critically reviewing enrollment on a regular basis, will monitor the accurate distribution of controls for both HIV and HBV, and make modifications as needed.

SANBS schedules blood drives up to 6 weeks in advance. Based on previous collections and expected turnout, SANBS is able to predict with a good degree of accuracy the number of blood collections that will be obtained from a given mobile or fixed site on a specific day. We will use

this information to guide the random selection of the clinics that research staff will target on a given day for control recruitment. A list of clinics or mobile sites based on the size of the clinic or mobile site from which cases are likely to come from will be created according to each SANBS zone and branch. From this list the clinic(s) (fixed and/or mobile) will be selected for study recruitment on a given day.

Within each branch, only a subset of clinics will be randomized. To determine the clinics from which controls will be recruited, we will use LAg Avidity assay results from the REDS-III Molecular Surveillance fast track study to identify the geographic area (clinic level), age and population group characteristics of donors with recently acquired HIV. Using 3 years of previous LAg Avidity results (2010 - 2012) to define the likely characteristics of donors who will meet our HIV case definition, we can enumerate the clinics that will be included in the randomization scheme from which we will seek to recruit control donors. The selected clinics will be determined in advance based on SANBS blood drive scheduling and included in the study management system so that research staff can plan for recruitment of potential controls on given days at specific venues. Using systematic sampling, we will randomly select donors presenting at a clinic who match the age and population group demographics of expected cases based on the analysis of the persons from the LAg Avidity study. However, if we are unable to recruit 3 controls from a given clinic we will seek to recruit the controls from other randomly selected clinics within the same SANBS branch. Particular clinics may not be appropriate for control recruitment due to reasons such as a very short period when a mobile clinic may be in operation or where there is no place at the collection site with a set up such that the donor can complete the ACASI in private. Research staff may have to make this determination based on visiting the actual collection venue or existing knowledge of particularly challenging venues for research study activities.

Every three months during the first two years of participant enrollment we will evaluate how well our controls match our enrolled cases with respect to the three key characteristics of geographic area, age, and population group. If the use of historical recently HIV-infected donors is not leading to correct frequency matching, we will shift the control recruitment to an approach which will rely either solely on the characteristics of the cases who enrolled in this study as the information used to determine targeted recruitment of controls, or on a combination of historical data and enrolled cases.

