**Cases Objectives 1 and 2:** The prospective enrollment will build on the existing notification mechanism with additional research nurse staff; we will consent and enroll donors during the retest visit during which they will receive pre-test counseling and be informed of the likelihood of being either HIV or HBV positive (**Consent in Appendix 2**). Following the provision of written informed consent and enrollment, participants will complete the ACASI questionnaire. Although

we plan to administer the ACASI questionnaire immediately following enrollment, we will provide study participants the option of returning to enroll and complete the interview at a later date.

For recent HIV (NAT yield and LAg Avidity recent) and recent HBV (NAT yield and HBsAg positive/anti-HBc negative) infections, all eligible cases will be approached for potential enrollment into the study since we anticipate that no more than 50% of those individuals with a recent infection will return to SANBS for their results following an index donation, but that we will have high success in enrolling these individuals into the study

**Controls:** Controls will be identified from among donors who are negative for all infections for which SANBS screens (HIV, HBV, HCV, and syphilis), and who are stratum-matched by blood centre, age within 5 years, population group. (**Consent in Appendix 3**).

We are proposing on-site recruitment of controls, meaning recruitment of potential controls following successful whole blood donation. To enhance our ability to recruit controls that will be able to be *post-hoc* matched on geographic region, population group, and age, we will select donation sites (both fixed and mobile clinics) with donor characteristics that are similar to donors who are incident HIV-positive. Following completion of the donation, we will invite random donors at predetermined collection sites that have similar demographic characteristics to enrolled cases, to participate in the risk factor study by completing the ACASI. Following completion of testing, donors who are negative for all infections for which SANBS screens will be included in the study.

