### **4.4 Measurement**

#### **4.4.1 Schedule of Measurement**

**Risk Factor Questionnaire:** A new questionnaire for the South Africa setting has been developed in English from a template previously used in Brazil for the REDS-II study. It assesses risk exposure over two intervals; ever and within the 6 months preceding the index donation. **Appendix 7** provides content for the risk factor questionnaire. The interview will be an audio computer-assisted structured interview (ACASI) as done successfully in a previous REDS-II and current REDS-III study in Brazil. Participants will be able to read and hear the questions using

ear phones for privacy. Interviews will be conducted using portable laptops so as to provide ease of access to the study participants. The ACASI interview will be conducted in a private location, ideally at a SANBS blood centre, but we will allow the interview to be conducted at the study participants' location of preference, such as at home. We propose to use 10 laptop computers (2 per zone) which will permit simultaneous interviews at different locations throughout SANBS. It will take approximately 30-45 minutes to complete the questionnaire. Interview data will be backed-up from the laptops onto a server or dedicated desktop computer at SANBS central offices on a daily basis, and uploaded weekly via a secure FTP site to the Data Coordinating Centre.

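### Clinics can be ruled out for controls but not for cases, so controls may under-represent some venues that supplied cases; the bias this could put into the Objective 1 odds ratios is of unknown size and direction

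*Protocol*

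**What the plan says.** All references are to the protocol.

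- **Purpose of the draw** (4.2.2, Control Recruitment and Enrollment): "To minimize selection bias, clinics within each branch will be randomly selected by the study statisticians".
- **Frame** (same section): "Within each branch, only a subset of clinics will be randomized". The clinics are enumerated from 2010–2012 LAg Avidity results, that is, from places where recently infected donors had been found.
- **Exclusion** (same section): "Particular clinics may not be appropriate for control recruitment due to reasons such as a very short period when a mobile clinic may be in". The other example given is a venue without privacy for the interview. These are examples only, so the list of reasons is open. On who decides: "Research staff may have to make this determination based on visiting the actual collection venue or existing knowledge of particularly challenging venues for research study". The section gives no criteria for the decision and no record of it.
- **Replacement** (same section): "if we are unable to recruit 3 controls from a given clinic we will seek to recruit the controls from other randomly selected clinics". The substitutes must belong to the same branch.
- **Check** (same section): three-monthly in the first two years of enrolment, on geography, age and population group.
- **Cases** (4.1.1 and 4.2.2, Participant Enrollment): a qualifying donation at any participating centre is eligible. All eligible cases are approached when they return for retesting, not at the clinic where they donated.
- **Interview place** (4.4.1): ideally a blood centre, but "we will allow the interview to be conducted at the study participants' location of preference, such as at home".

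**The concern.** A case-control comparison needs controls drawn from the donors among whom the cases arose. Here a venue filter acts on one side only. A donor infected at a brief mobile drive can become a case, while the uninfected donors at that drive have no chance of becoming controls if staff judge the venue unworkable.

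The grounds for exclusion relate to the kind of venue, and the kind of venue may relate to the kind of donor. Matching on branch, age and population group does not restore a missing venue type, and a check on those characteristics can look satisfactory while that type is absent. Section 4.8.1 itself calls the similarity of behavioural exposures between clinics substantially uncertain. Its response is to enrol more controls, which improves precision but does not remove selection bias. The same controls serve the HBV comparison, so Objectives 1a and 1b both inherit the problem.

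**Working it through.** **1. The plan's own figures.** Table 8 (300 cases, 900 controls) gives detectable odds ratios of 1.94, 1.74 and 1.65 at control exposures of 0.15, 0.20 and 0.25, each with cases 10 points higher. Directly from those proportions:

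- (0.25/0.75)/(0.15/0.85) = 1.889
- (0.30/0.70)/(0.20/0.80) = 1.714
- (0.35/0.65)/(0.25/0.75) = 1.615

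The tabled values are 1.5% to 2.7% higher, and means of simulated odds ratios are 1.91, 1.73 and 1.63. The table is not in dispute and serves only as a yardstick.

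**2. The two recruitment routes side by side.**

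| | Cases | Controls |
|---|---|---|
| Venue filter | none stated | staff may rule a clinic out |
| Where enrolled | recall visit | collection site |
| If the venue is unworkable | no effect on eligibility | another randomly selected clinic in the branch, type not specified |
| Venue type in the matching check | no | no |

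**3. Illustration of size.** Two inputs are not in the protocol and are assumed here: *s*, the share of case-source donors at ruled-out venues (10%, 20%, 40%), and exposure at retained and ruled-out venues (15% and 25%, borrowed from the ends of Table 8's control range). The true odds ratio is set to 1.

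Case exposure p = (1 − s) × 0.15 + s × 0.25. Control exposure = 0.15. Apparent OR = [p/(1 − p)] / (0.15/0.85).

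- s = 0.10: p = 0.16; OR = 0.1905/0.1765 = 1.08
- s = 0.20: p = 0.17; OR = 0.2048/0.1765 = 1.16
- s = 0.40: p = 0.19; OR = 0.2346/0.1765 = 1.33

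With the gap reversed (25% retained, 15% ruled out), p = 0.24, 0.23, 0.21, and dividing p/(1 − p) by 0.25/0.75 gives 0.95, 0.90 and 0.80.

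**4. False-positive rate.** This uses a two-sided 5% test of two independent proportions, 300 against 900, with d = p − 0.15, SE0 the pooled and SE1 the unpooled standard error. The rejection probability is Φ((d − 1.96·SE0)/SE1) + Φ((−d − 1.96·SE0)/SE1).

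- s = 0.10: SE0 = 0.0240, SE1 = 0.0243; about 7%
- s = 0.20: SE0 = 0.0241, SE1 = 0.0247; about 14%
- s = 0.40: SE0 = 0.0244, SE1 = 0.0256; about 38%

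**5. Wider assumptions.** Take retained exposure 0.20, ruled-out exposure 0.10 to 0.40 and s up to 40%.

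- Lower end: p = 0.6 × 0.20 + 0.4 × 0.10 = 0.16; OR = (0.16/0.84)/0.25 = 0.76
- Upper end: p = 0.6 × 0.20 + 0.4 × 0.40 = 0.28; OR = (0.28/0.72)/0.25 = 1.56
- A true OR of 1.714 would appear as 1.31 to 2.67 (1.714 times the unrounded 0.762 and 1.556)
- If ruled-out exposure is also 0.20, the OR stays at 1.00 and there is no bias

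**The case against.** **Replacement is random.** A reader might infer that staff choose the substitute clinic. The text does not say so: staff judge only whether a venue is workable, and the substitute is another randomly selected clinic in the branch. Branch-level geography is therefore kept. Venue type is not.

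**Exclusion may come before the draw.** A reader might infer that clinics are dropped after being drawn. Existing knowledge of a venue could instead narrow the frame beforehand, while a visit suggests afterwards. The protocol does not settle it, but the mismatch with cases arises either way.

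**There is no clear contradiction over interview place.** It is tempting to say that the privacy ground conflicts with the freedom to be interviewed elsewhere or later. The promise that "we will provide study participants the option of returning to enroll and complete the interview at a later date" sits in the paragraph on cases, and the similar sentence in section 4.10 follows a statement about notification visits. Only the general sentence in 4.4.1 arguably reaches controls, and it is a permission. Requiring privacy for a questionnaire on sexual behaviour is reasonable.

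**The size is assumed.** The 15% and 25% are alternative values for the whole control group, not a measured gap between venues within matched strata. The 40% share has no support in the protocol, and a very short drive would plausibly supply few donors. This stands in full.

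**Existing safeguards.** Section 4.2.2 promises regular review of the control distribution and changes as needed. It also glosses geographic area at clinic level when describing the historical data, and elsewhere speaks of matching by blood centre. A check at clinic level would show cases without matching controls. But replacement is allowed anywhere in the branch, section 4.3 speaks of region, and no step addresses venue type. Allowing for clinic clustering in the analysis corrects variance, not selection.

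**Deferred interviews carry their own cost.** Recalled donors return at only 49% (HIV, Table 5) and 28% to 37% (HBV, Table 7). Uninfected donors have no result to return for. Making off-site interviews compulsory could exchange venue selection for self-selection.

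**Conclusion.** The concern holds in a limited form. A venue filter based on staff judgement applies to controls and not to cases, and it cuts into a draw introduced to limit selection bias. Neither the replacement rule nor the matching check preserves venue type. Controls may therefore under-represent some venues that supplied cases.

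Whether this biases Objectives 1a and 1b depends on exposure differing between venues within age, population-group and branch strata. The protocol gives neither that difference nor the number of affected clinics, so size and direction are unknown. Under the stated assumptions a null odds ratio appears as 1.08 to 1.33, or 0.95 to 0.80 with the gap reversed. At the low end that is small beside the detectable 1.65 to 1.94; at the high end it is not negligible.

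The documents do not support the stronger conclusions that controls definitely fail to represent the source donors, or that every behaviour varying by venue will show a false association. The reason to act is practical: if exclusions are not recorded from the first recruitment day, the effect may not be assessable afterwards, and a later analysis plan cannot recreate the record.

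**What to change.** 1. **Same-type replacement.** When a clinic is unworkable, take the next clinic of the same type (fixed or mobile) in the same branch from a reserve list that the study statisticians have put in random order in advance.
2. **Log.** From the start of recruitment, record the code and reason for every clinic ruled out, whether before or after the draw.
3. **Sensitivity analysis for Objectives 1a and 1b.** Repeat the main models leaving out cases whose index clinic was ruled out for controls. Appendix 7 item A3 already collects the clinic code, and the donor table in Appendix 6 has a field for the clinic where the unit was collected.
4. **Optional.** Where the only obstacle is the lack of a private room, off-site interview under section 4.4.1 may be offered to controls. It should not be mandatory, because deferral can add non-response.

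The cost is slight extra logistics, one log field, and one extra model with somewhat fewer cases and so somewhat wider intervals.

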### **Objective 3 Prospective Cohort**

From the group of donors identified as having incident and elite controller HIV infections, a smaller convenience group of willing participants will be enrolled into Objective 3 of the study. The planned study activities for Objective 3 participants are shown in Figure 3. Enrollment will take place at the time these donors attend the post-test HIV counseling visit, or, where the donors are not assessed to be ready for enrollment at that time, shortly thereafter.

Donors who agree to participate in the study will be fully consented as to the requirements of Objective 3 of the study. Donors who consent will then be enrolled on to the study and specimens collected for CD4, viral load and cytokine profiling as well as PBMC preparations. Samples will be labeled, packed and transported according to SANBS standard operating procedures which comply with all local requirements for the transportation of bio-hazardous material. All samples will be sent to the Donation Testing Laboratory in Constantia Kloof, Gauteng from where it will be sent to the appropriate laboratories for additional testing as required. Following sample collection, the participant will complete the ACASI questionnaire for Aim 1 of this study. In addition, at each follow-up visit a short questionnaire will be completed just after collection of the blood samples, using a Teleform-style form. The content of this questionnaire will assess healthcare-seeking behavior and any medicines or natural remedies the study participant has taken or initiated since the last study visit, possible side effects of these medicines and other exposures that may influence the viral dynamics of early HIV infection. Women will also be asked if they are currently pregnant.

Clear information will be provided to participants on the visit schedule, including the enrollment visit expected to occur approximately 1 month after the index donation visit and repeat sampling at 3 follow-up visits at 2, 3, and 6 months following the index blood donation. The importance of adherence to the visit schedule will be emphasized, and full contact details recorded for each participant. Follow-up contact of these donors will be centrally coordinated and each MLO notified when a donor in the prospective cohort must be contacted to return for follow-up samples. Donors will be contacted via telephone. During this telephone call, an appointment will be made for the donor to return for follow-up testing at a specific date, time and venue. If the donor cannot, after repeated attempts, be contacted via telephone, a letter and text message will be sent to the donor. If the donor were to respond to the letter or text message, an appointment will be confirmed for that donor. Letters confirming the date, time and venue of the appointment will be sent to each donor and will be followed by a text message the day before the appointment. All successful and unsuccessful contact attempts with the participant will be documented in a Contact Log, as described above. At scheduled follow-up visits, participant samples will be collected, labeled and sent to the Donation Testing Laboratory in Constantia Kloof as detailed above.

Every year SANBS identifies approximately 50 NAT-only HIV infections. With a planned enrollment period of 3 years and an enrollment target of 50 HIV NAT-only infections for

Objective 3, and assuming 50% enrollment, we anticipate two years of accrual to meet the enrollment goal, and allow 6 months of prospective follow up.

[figure not shown]
The number of elite controllers identified each year has been increasing (Table 4). Projecting that the proportion of donors who are elite controllers in 2014 -2017 will be similar to those observed in recent years and assuming a 50% enrollment rate it will be feasible to enroll 20 elite controllers during the first 2.5 years of the study, allowing for a tail-end follow-up of 6 additional months of return follow-up visits during the same time as the Objective 1 and 2 enrollment takes place.

Table 4. Number of elite controller HIV infections identified each year by SANBS while ID-NAT for HIV has been in use.

Year	Elite Controllers
2007	2
2008	11
2009	8
2010	9
2011	13
2012	21
2013 (January - June only)	11
Total	75

All of the donors who participate in the study will be nominally compensated for travel expenses and inconvenience of study participation for each study visit in Objectives 1, 2 and 3. The reimbursement amount will be approved in accordance with the local South African IRB, and will represent an amount in local currency equivalent to approximately USD\$10.

Figure 3 Objective 3 Prospective cohort testing and study entry.

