National surveillance of HIV risk in Africa has traditionally focused on prevalent rather than incident infection; this holds implications for prevention planning and evaluation. Prevalent infection, although more amenable to measure, provides a skewed assessment of disease profile, particularly in view of expanding antiretroviral coverage that prolongs survival. Incidence surveillance reflects a more accurate representation of currently relevant risk factors given the proximity to recent infection. This has consequently been adopted effectively in the United States and other industrialized countries. Unfortunately, there is a lack of HIV or HBV incidence data, particularly in resource-poor settings and specifically in sub-Saharan Africa where these diseases are prominent. Furthermore, comparative analyses of incident vs. prevalent risk factors are few. The assumption that incident risk factors parallel those of prevalent infection is not necessarily accurate. This was demonstrated in a study by McFarland et al in Zimbabwe, whereby age and marital status reversed their direction of association with respect to HIV incidence vs. prevalence. This may reflect a shift in the epidemiology of HIV infection.

The use of ID-NAT by SANBS provides a unique opportunity to identify very recent HIV and HBV infections with a high degree of accuracy. Universal screening of donations by parallel testing for nucleic acids and serological assays can accurately gauge incidence given known thresholds of detection by NAT and serology. In the event that HIV is newly acquired, positivity by ID-NAT (5-10 days post-infection) precedes antibody positivity (detectable at about 21 days) by over 10 days; these so-called “NAT-yield” HIV infections refer to incident or recently acquired infections that have not yet stimulated an antibody response. Over more than 5 years (2005-2010), 165 HIV NAT-yield incident positive cases have been identified at SANBS.

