To minimize any community rumors or individual anxieties linking the research to HIV status, recruitment scripts and study informational materials will emphasize that both HIV-positive, HBV-positive, and HIV and HBV-negative participants are being enrolled in order to identify and compare prevailing risk factors among the positive and negative groups. All donors will complete the same ACASI questionnaire.

**Objective 3 Participants:** Selected donors with incident HIV infections who were identified and enrolled during the first two years of Objective 1a and 2a recruitment will be prospectively enrolled into Objective 3 of the study. Participants in Objective 3 will be a subset of Objective 1a and 2a participants who meet eligibility criteria and are willing to participate in this objective. Elite controllers will include those identified in the first 2.5 recruitment years of the study. Donors will be consented and enrolled either during the post-test HIV counseling visit or shortly thereafter timed with Objective 1 enrollment and specimens collected on the day of enrollment and at 3 follow-up visits for CD4, viral load and cytokine profiling as well as PBMC preparations (**Consent in Appendix 4**). The total volume of blood collected at each follow-up visit will not exceed 48 mL.

**Study Locations:** The study will be located in geographic areas within the SANBS catchment where the proportion of donors with HIV and HBV infectious markers is high and where there is documented evidence of good success in notifying donors. We will conduct the study in 5 locations in 4 Provinces; Gauteng (Johannesburg and Pretoria), KwaZulu Natal (Durban), Mpumalanga Province and the Eastern Cape Province. For operational purposes, SANBS divides the Gauteng Province into 3 operational zones, namely “Egoli”, “Vaal” and “Northern”, with Johannesburg the main metropolitan area in Egoli and Pretoria the main metropolitan area in the Northern zone.

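### The Objective 3 projection of 50 NAT-yield participants in two years applies an all-SANBS infection count to a five-zone study; the protocol's own inputs give about 40, and the intake window is stated inconsistently

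*Protocol*

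**What the plan says.** The projection stands in the Protocol under Objective 3 Prospective Cohort. Its base is the whole service: "Every year SANBS identifies approximately 50 NAT-only HIV infections". To this it applies one fraction and one duration: "assuming 50% enrollment, we anticipate two years of accrual to meet the enrollment goal". The goal is 50 NAT-only participants.

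Other places in the protocol bear on it:

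- **Zones.** Section 4.2.2 Participant Enrollment, Study Locations: "We will conduct the study in 5 locations in 4 Provinces". Johannesburg (Egoli), Pretoria (Northern), KwaZulu Natal, Mpumalanga and the Eastern Cape are named. Vaal and Free State/Northern Cape are not.
- **Yearly count.** Section 3: "Over more than 5 years (2005-2010), 165 HIV NAT-yield incident positive cases have been identified at SANBS". Table 3, titled "Demographic characteristics of HIV NAT only and HBV NAT only positive donors at SANBS for the years 2006 – 2010", has 300 HIV donors. Section 4.8.1 repeats about 50 a year.
- **Participation.** Section 4.8.1 uses about 50% for Objective 1. Section 4.2.2 says that no more than half of recently infected donors are expected to return. Objective 3 is a willing subset of the Objective 1a and 2a participants.
- **Intake window.** Section 4.2.2, Objective 3 Participants, describes incident cases "identified and enrolled during the first two years of Objective 1a and 2a recruitment". On the other group it says: "Elite controllers will include those identified in the first 2.5 recruitment years of the study". Section 4.1 makes both groups eligible if identified between mid-2014 and mid-2017, and places accrual, enrolment and follow-up together in April 2014 to March 2017.

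**The concern.** The projection meets its target with no margin, and two of its inputs favour it. The count covers seven zones while recruitment covers five. The 50% is spent on getting a donor back and into Objective 1, so nothing is left for donors who join Objective 1 but decline further blood draws and visits. No allowance is made for loss over the visits at 2, 3 and 6 months either.

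At stake is the size of a scarce cohort meant to describe early viraemia and immune response. The window adds to this. If NAT-yield intake stops at two years, six months of possible recruitment go unused, although elite controllers with the same last visit are recruited through them.

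**Working it through.** **1. The protocol's figure.** Infections per year × enrolment fraction × years = 50 × 0.50 × 2 = 50. It reproduces exactly, with all zones counted and every enrolled NAT-yield case joining Objective 3.

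**2. Share in the study zones (Table 3, HIV column).** KwaZulu Natal 83 + Egoli 43 + Eastern Cape 24 + Mpumalanga 35 + Northern 52 = 237. 237/300 = 0.79.

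**3. Yearly counts in the protocol.** About 50 (Objective 3 Prospective Cohort; Section 4.8.1). 300/5 = 60 (Table 3). 165/5 = 33 at most (Section 3, since the period is given as more than five years).

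**4. Expected five-zone enrolment** = rate × 0.79 × 0.50 × years, with nobody refusing Objective 3:

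| Rate per year | 2 years | 2.5 years | Enrolment needed for 50 in 2 years |
|---|---|---|---|
| 33 | 26.1 | 32.6 | 50/(33 × 0.79 × 2) = 96% |
| 50 | 39.5 | 49.4 | 50/(50 × 0.79 × 2) = 63% |
| 60 | 47.4 | 59.3 | 50/(60 × 0.79 × 2) = 53% |

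At the planning rate of 50 the two-year shortfall is (50 − 39.5)/50 = 21%. Across the three counts it runs from (50 − 47.4)/50 = 5% to (50 − 26.1)/50 = 48%.

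**5. Sensitivity to the return rate (Table 6, six-month totals).** Weighting each study zone's fraction counselled by SANBS by its Table 3 count:

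(83 × 124/172 + 43 × 32/139 + 24 × 25/80 + 35 × 44/118 + 52 × 52/120)/237 = 47.6%.

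Two years then give 24.8, 37.6 and 45.1 at 33, 50 and 60 a year. Adding donors counselled outside SANBS raises the weighted rate to 57.7%, which gives 50 × 0.79 × 0.577 × 2 = 45.6 and, at 60 a year, 54.7. The Egoli percentages in Table 6 match its outside-SANBS row; using 35 instead of 32 moves 47.6% only to 48.0%.

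**6. Refusal.** If a fraction *j* of enrolled NAT-yield cases join Objective 3, every figure is multiplied by *j*. The protocol gives no *j*. At 50 a year, each ten percentage points of refusal removes about 4 of the 39.5, or about 5 of the 49.4.

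**7. Window.** Two and a half years from April 2014 ends in September 2016. A donor identified then has the six-month visit in March 2017, the last month of the study period in Section 4.1. The mid-2017 end date in that section would put six-month visits after that period.

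**The case against.** The strongest reply is that the 50% may be cautious. Section 4.2.2 (HIV) says that SANBS emphasises notifying NAT-yield donors, that its rates pool incident and prevalent infections, and that success should rise with added research staff. In five zones, 53% at 60 a year would be enough. Mpumalanga rose from 14–25% in January to March 2012 to 54–61% in April to June. This stands as a reason not to call the target unreachable. It does not rescue the projection: no size is given for the improvement, and the same paragraph still expects about 50%.

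A reader might infer that no set of the protocol's inputs reaches 50. That is not supported. Sixty a year in all zones gives 60, and counting outside-SANBS counselling gives about 55 in five zones at 60 a year, though whether such donors could enrol is unclear.

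A reader might also infer that NAT-yield donors found in months 25 to 30 will be refused. The two years in the Objective 3 text is an expectation, and Section 4.1 leaves eligibility open to mid-2017. Only the paragraph on Objective 3 participants reads as a limit. The documents show an inconsistency, not a rule of refusal.

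Finally, the target is worded as approximate, Section 4.9 calls the analysis primarily descriptive, and no power or precision claim rests on 50. That stands, and it limits the severity.

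**Conclusion.** The point holds as a minor feasibility shortfall. The arithmetic is sound, but its base does not match the study area. On the protocol's planning inputs, two years in five zones give about 40 NAT-yield participants instead of 50 (21% fewer). Its conflicting yearly counts give about 26 to 47. All are ceilings at 50% enrolment, because refusal of Objective 3 is not allowed for; later loss to follow-up would reduce complete series further.

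It would go too far to say that the cohort will be a quarter to a half smaller. The large end depends on the Section 3 count, which is not the planning input. A cohort of about 40 still allows the descriptive aim to be met.

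The result assumes that the 2006–2010 regional shares still apply. The Table 6 sensitivity also assumes that rates for all HIV-positive donors in early 2012 carry over to NAT-yield donors. Donors under 18 are excluded, and Table 3 places them in a 16–19 group of 16.3%. Removing them would lower the counts by between 0 and 16%.

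**What to change.** Reconcile Section 4.1, the Objective 3 Prospective Cohort text and the Objective 3 Participants paragraph to a single NAT-yield intake window of 2.5 years, as for elite controllers.

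In the same edit, restate the projection for the five study zones with one reconciled yearly count and an explicit fraction of enrolled NAT-yield cases expected to join. At 50 a year and 50% this reads about 40 in two years or at most about 49 in 2.5 years (about 33 to 59 across the protocol's yearly counts), each multiplied by the joining fraction. The longer window roughly restores the target only if nobody refuses, so the text should not present 49 as an expectation with room to spare.

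The cost is a few sentences. Intake and visits for elite controllers already cover this period. The drawback is that the last NAT-yield follow-up data arrive at the end of year 3.
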